## 12.0 Procedures Involved\*

12.1 *Provide a description of **all research procedures or activities** being performed and when they are performed once a subject is screened and determined to be eligible. Provide as much detail as possible.*

*NOTE: This should serve as a blueprint for your study and include enough detail so that another investigator could pick up your protocol and replicate the research. For studies that have multiple or complex visits or procedures, consider the addition of a schedule of events table in in your response.*

Response:

The proposed study will occur during 2019-2020 with data collection occurring for about 17 months. Recruitment and data collection will occur on a rolling basis, with individual participants' involvement being for about 6 weeks. All data will be collected online or via phone.

Following completion of initial screening, participants will complete consent procedures and a HIPAA form for their physician to confirm their diabetes/prediabetes diagnosis, or specific health characteristics that increase their risk of developing type 2 diabetes in accordance with the American Diabetes Association Type 2 Diabetes Risk Test [see Consent and HIPAA form]. Physicians will be contacted using their modality of choice; this may include phone, email, fax via efax.com, or in-person communication). Participants will be mailed their Clincard for participant payment and move on to baseline procedures: a questionnaire [See attachment: Questionnaires], a baseline shopping trip and receipt submission, and a brief phone interview with questions about their shopping trip [See attachment: Phone interview]. Any participant who does not follow guidelines for baseline procedures will not proceed to randomization (but will be compensated for their time, as detailed below).

Participants' baseline shopping trips will be in-person at their usual grocery store. Following their baseline shopping trip, participants will submit a photograph of their household receipts via email and of a receipt information form (attached). Study staff will contact participants to remind them about this if photographs are not received within the time frame discussed during consent procedures. When the photos are received, study staff will mail participants their Clincards to be used for participant payments and will contact participants via phone to ask follow-up questions and share with participants their assigned study group [See attachment: Phone interview].

Participants will be randomized in blocks to the *Online*, *Defaults*, or *Control* group, stratifying by diabetes status (diabetes vs. increased risk for developing type 2 diabetes). Study staff will consult a pre-populated spreadsheet in order to determine the study group of each participant. Participants in the *Online* and *Defaults* groups will receive instructions on how to access an online grocery shopping account on Instacart ([www.instacart.com](http://www.instacart.com)). Instacart is a platform through which customers can grocery shop online and have their groceries delivered within a designated window. Many leading grocery retailers offer grocery shopping via Instacart, including Tops and Wegmans, both of which are based in Western New York; there are approximately 250 locations of these chains throughout the Northeastern United States, including but not limited to: New York, New Jersey, Pennsylvania, and Massachusetts.

Accounts will be set up for the participants by study staff, with shared access. Participants will enter their credit/debit card information and purchase their own groceries, to enhance ecological validity. Only the last 4 digits of the participant's credit or debit card number will be visible to study staff when accessing the account to download receipt data (*Online* and *Defaults* groups) and populate the default cart (*Defaults* group). During the 3 weeks that follow randomization, *Control* group participants will be asked to shop as they normally would, in-person at Tops or Wegmans. Those in *Online* and *Defaults* groups will be asked to shop as they normally would but using their grocery store's Instacart platform. In addition, the *Defaults* group will be told that their cart will be pre-filled with items that conform to a diet appropriate for diabetes management, prevention, and overall health. The items will correspond to the DASH diet. All participants will receive 3 DASH-diet friendly recipe cards each week, and the items in the *Defaults* group's carts will correspond to the recipes. The default cart will be populated by study staff after study group assignment and will be re-populated to prepare for the next purchase each time the participant completes a shopping trip. During the post-test week, all participants will be asked to shop using the method of their choice (in-person, online); no default carts or recipe cards will be given. At post-test participants will also complete a Food Frequency Questionnaire as well as an Exit Questionnaire (see attachment: Questionnaires).

Based on inclusion criteria, we expect each participant to shop at least once during each of the three intervention weeks; participants can shop more than once per week if this is what they typically do. Either way, they will be instructed to continue to submit their receipts from all household grocery shopping at

Tops/Wegmans via email as done at baseline. Participants will be prompted weekly, reminding them to shop as they normally would and to ask whether the household has completed any shopping trips without submitting receipts. Participants will also be asked about foods purchased from other locales during phone interviews following submission of receipts each week (See attachment: Phone interview). Although receipts are downloadable from Instacart in the intervention groups and weeks, we will collect these receipts from participants as well, for consistency and as an indicator of the extent to which the number of submitted receipts corresponds to the number of actual receipts, to further inform feasibility for subsequent larger-scale work.

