### Data to be collected include:

- \*Confirmation of diabetes status or diabetes risk status (see attachments: Consent and HIPAA Form)
- \*Demographic questions collected at baseline (see attachment: Questionnaires)
- \*Changes in daily routine, perceived stress and loneliness questions at baseline (see attachment: Questionnaires)
- \*Calories, carbohydrates, sugar (total sugar and/or added sugar), and food groups each week of the 5-week shopping period, from receipts (see additional details below)
- \*Information on which purchased items will be consumed by the participant and information about foods acquired from other sources besides the target grocery store that week (administered after each shopping trip, see attachment: Phone interview)
- \*Dollars spent on groceries at each time point, from receipts (each week)
- \*Dietary intake from a Food Frequency Questionnaire (see details below and attachment: Questionnaires; collected at post-test)
- \*Exit questionnaire (completed at the end of the study; see attachment: Questionnaires)

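### Section 12.1 collects baseline as one shopping trip and discloses the study group once its receipts arrive, while other text counts baseline as a full week of household receipts; the two must be reconciled

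*Combined protocol and SAP*

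**What the plan says.** **Baseline, Section 12.1.** Baseline consists of a questionnaire and then "a baseline shopping trip and receipt submission, and a brief phone interview with questions about their shopping trip". On place, "baseline shopping trips will be in-person at their usual grocery store". On receipts, "Following their baseline shopping trip, participants will submit a photograph of their household receipts via email". The next step depends on an event, not on the calendar: "When the photos are received, study staff will mail participants their Clincards to be used for participant payments and will contact participants via phone", both to ask follow-up questions and to "share with participants their assigned study group". No length in days is given for baseline.

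**Intervention weeks, Section 12.1.** Each participant is expected to shop at least once a week, and "participants can shop more than once per week if this is what they typically do". Whatever the number of trips, "they will be instructed to continue to submit their receipts from all household grocery shopping at" Tops/Wegmans, by email and in the same manner as at baseline. A weekly prompt asks whether any household trip has gone without a submitted receipt. No such prompt is described for baseline.

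**Unit of analysis, Sections 12.2 and 19.1.** The data list calls for calories, carbohydrates, sugar and "food groups each week of the 5-week shopping period, from receipts". Five weeks is one baseline week, three intervention weeks and one post-test week. The mixed models in 19.1 use group, time and their interaction. The primary comparisons are between groups at post-test; differences between groups in change are examined as well.

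**The concern.** The trip-and-call sequence and the five-week count describe different baselines. Take a household that shops on Monday and Friday. Under the sequence in 12.1 it could send Monday's receipt, be telephoned and learn its group before Friday. Baseline would then hold Monday only, while every later week holds both trips. Entry under Section 8.1 requires shopping at Tops or Wegmans at least weekly, so such households are eligible.

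For them, totals of calories, carbohydrates, sugar and dollars would rise from baseline to follow-up with no change in behaviour. The time effect and any within-arm change would carry that rise. Baseline would also be a poorer reference for the group-by-time tests, which bear on hypothesis 1b in Section 2.2. The trips left over in the baseline week would be made with the group already known.

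**Working it through.** **1. Does the text settle the unit?** Pointing to one trip: the singular trip in 12.1, the interview about that trip, and a disclosure call triggered by photos. Pointing to a week: the reference to household receipts, the statement that later submission continues baseline practice, the five-week count in 12.2, and the statement in Section 5.1 that household receipts are collected throughout. No section states a window or how trips are summed to a time point. The text is in conflict; it does not settle on one trip.

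**2. Are arm contrasts biased?** On the raw scale, the difference in change between arms A and C is (post_A − post_C) − (base_A − base_C). Baseline is collected before disclosure and in the same way in every arm, so the second bracket has expectation zero even for a one-trip baseline. Post-test values are untouched. A simulation with no treatment effect (18 per arm, 1 to 3 trips a week, one-trip baseline, 3,000 replicates) agrees: control totals rose by about 100%, the between-arm difference in change was about 0, and type I error was 0.050 for change and 0.051 for post-test alone.

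**3. Size of the artificial rise.** Let p be the share of households with more than one trip a week, and let their first trip average 60% of the week. Neither figure is in the documents. With true weekly mean 1, the one-trip baseline mean is (1 − p) + 0.6p = 1 − 0.4p, so the rise is 1/(1 − 0.4p) − 1.

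| p | Baseline mean | Apparent rise |
|---|---|---|
| 0.2 | 0.92 | 8.7% |
| 0.4 | 0.84 | 19.0% |
| 0.6 | 0.76 | 31.6% |

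**4. Loss of precision in change.** Further assumptions: weekly totals are log-normal with log-SD 0.5 and within-household log correlation 0.6. With mean 1, V = exp(0.25) − 1 = 0.284 and C = exp(0.15) − 1 = 0.162. The full-week correlation is C/V = 0.57 and the change variance is 2(V − C) = 0.244.

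For a one-trip baseline with first-trip fraction S (S = 1 in once-weekly households), the baseline variance is E(S²)(1 + V) − E(S)², and the covariance with follow-up is E(S)·C. If S is uniform on 0.3 to 0.9 in multi-trip households, its variance there is 0.6²/12 = 0.03 and E(S²) = 1 − p + p(0.36 + 0.03).

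| p | E(S²) | Baseline variance | Covariance | Correlation | Change variance | Increase |
|---|---|---|---|---|---|---|
| 0.2 | 0.878 | 0.281 | 0.149 | 0.53 | 0.267 | 9% |
| 0.4 | 0.756 | 0.265 | 0.136 | 0.50 | 0.277 | 13% |
| 0.6 | 0.634 | 0.236 | 0.123 | 0.47 | 0.275 | 12% |

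If S is exactly 0.6 in every multi-trip household (variance 0), the same formulas give increases of 6%, 7% and 3%. The result depends on how much the first-trip fraction varies; about 6% to 14% covers most of the settings tried.

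**5. Link to the stated sample size.** Section 19.2 gives 15 for d = 0.96 and 54 for d = 0.44. Both reproduce as total N for a group-by-time interaction with 3 groups, 2 measurements, correlation 0.5 and f = d/2, using noncentrality N·f²·2/(1 − ρ). For 54: 54 × 0.22² × 2/0.5 = 10.45, power 0.81. For 15: 15 × 0.48² × 2/0.5 = 13.82, power 0.84. The next smaller multiples of three, 51 and 12, give 0.78 and 0.71. That model is inferred; the document does not name it.

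If it was the basis, the calculation leans on the baseline-to-follow-up correlation. In a harsher case, where every household makes 2 or 3 interchangeable trips a week and the week-to-week correlation is 0.5, the correlation of one trip with a week is 0.41 or 0.35. Power at 54 is then about 0.74 or 0.70, and the N required is 63 or 69.

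**The case against.** The best defence is that a weekly baseline was plainly intended. The instruction for later weeks is to continue what was done at baseline, baseline is called a period, and five weeks of receipts are counted. Section 12.1 also mentions a time frame for photographs discussed at consent, and receipt-collection instructions are attached but not included in the document. A window may be stated there. Nothing says that later baseline-week receipts are refused or that the call is immediate.

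This stands to the extent that a reader might infer from 12.1 that baseline and follow-up are definitely different measures. The documents do not support that; they conflict. Nor do they support saying that trips after disclosure belong to no period: 12.1 places the intervention in the three weeks following randomisation, which could take them in. The documents also do not say how many households shop more than once a week; such trips are permitted, and only one a week is expected.

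The defence does not remove the problem. A full baseline week cannot be captured before disclosure if the call follows the first trip's photos. Continuing as at baseline can also be read as referring only to the emailing of receipts. Section 12.1 is meant to be detailed enough for another team to replicate the study, and staff following its sequence would collect one trip.

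The consequence is limited, as the defence says: the primary comparisons are at post-test, and no within-arm change is named as an endpoint.

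**Conclusion.** The point holds as a conflict within the protocol that should be resolved. Followed literally, the baseline sequence in 12.1 gives multi-trip households a partial first week, contrary to the weekly unit used in 12.2.

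The harm falls on the time effect and on within-arm changes in totals: an artificial rise of about 9% to 32% for 20% to 60% multi-trip households with a first trip of about 60% of the week. Change-by-group tests lose modest precision, with variance up by about 6% to 14% in most of the settings tried and as little as 3% if the first-trip fraction never varies. Trip frequency, trip share, log-SD and correlation are all assumptions. The effect on the DASH score cannot be stated, because its scoring for purchases is not given.

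A reader might infer that the trial's treatment comparisons are biased. They are not: the post-test contrast does not use baseline as its outcome, and the expected between-arm difference in change is unaffected. Once-weekly shoppers are measured alike on either reading.

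**What to change.** In Section 12.1:

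- Define baseline as a fixed 7-day window in which all household Tops/Wegmans receipts are submitted, as in each later week. This also resolves the mismatch between the usual grocery store at baseline and Tops/Wegmans afterwards.
- Use the same prompt about unsubmitted receipts as in the intervention weeks.
- Make the call that discloses the study group, and start intervention week 1, only after the window closes.
- State that each time point is the sum over all trips in its week.

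The cost is protocol and script wording. Disclosure moves by up to 6 days, which fits the stated participation of about six weeks around five shopping weeks. A slightly longer run-in may lose a few more participants, all before they know their group. The change has to be made prospectively, because baseline receipts that were never collected cannot be recovered.

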### 1.0 Study Summary

Study Title	Improving adherence to a diabetic diet with a grocery shopping intervention
Study Design	
This study has an experimental design. Participants will be randomly assigned to 1 of 2 interventions or a control group in which they will shop in-person as usual. Stratification factors will be sex and diabetes status: diabetic vs. at risk for type 2 diabetes, defined as a diagnosis of prediabetes or meeting criteria for increased risk of developing type 2 diabetes in accordance with the American Diabetes Association Type 2 Diabetes Risk Test. In all groups, recipe cards that follow the evidence-based DASH diet will be provided; recipes correspond to dietary recommendations for patients with type 2 diabetes or at increased risk of developing type 2 diabetes. The Online intervention will utilize online grocery shopping (shopping at a local grocery store via Instacart) to promote healthier purchasing, removing visceral factors that can lead to impulse purchases in stores. The Defaults intervention will augment this intervention, showing participants a default cart when they log into their accounts. They will be told that their cart has been filled with items that conform to a diet for diabetes prevention, management, and overall health and can be used to make the recipes from the provided recipe cards, and that they may modify it as they like.
 
At baseline, all participants will complete a survey online or via phone and then will grocery shop in-person as usual. Participants will then be randomized and receive further instructions. For the next 3 weeks, they will receive recipe cards and shop in accordance with their assigned study group. The following week (post), they will shop using their preferred mode (in-person or online) and complete a survey again. Household receipt data will be collected throughout

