## 5.0 Study Design\*

5.1 Describe and explain the study design (e.g. case-control, cross-sectional, ethnographic, experimental, interventional, longitudinal, observational).

Response:

This study has an experimental design. Participants will be randomly assigned to 1 of 2 interventions or a control group in which they will shop in-person as usual. Stratification factors will be sex and diabetes status: type 2 diabetic vs. at risk for type 2 diabetes, defined as a diagnosis of prediabetes or meeting criteria for increased risk of developing type 2 diabetes as determined by the American Diabetes Association Type 2 Diabetes Risk Test. In all groups, recipe cards that follow the evidence-based DASH diet and correspond to dietary recommendations for diabetic patients will be provided. The *Online* intervention will utilize online grocery shopping (shopping at a local grocery store via Instacart) to promote healthier purchasing, removing visceral factors that can lead to impulse purchases in stores. The *Defaults* intervention will augment this intervention, showing participants a default cart when they log into their accounts. They will be told that their cart has been filled with items that conform to a diet appropriate for diabetes prevention, management, and overall health and can be used to make the recipes from the provided recipe cards, and that they may modify it as they like.

At baseline, all participants will complete a survey online or via phone and then will grocery shop in-person as usual. Participants will then be randomized and receive further instructions. For the next 3 weeks, they will receive recipe cards and shop in accordance with their assigned study group. The following week (post), they will shop using the method of their choice (in-person, online) and complete a survey again. Household receipt data will be collected throughout the study. The baseline period will also serve as a run-in period, and participants who do not comply with study guidelines for baseline procedures (including guidelines for receipt submission) will not be randomized for further participation. Primary analyses will examine intervention effects on grocery purchases, with additional analyses on spending and dietary intake. All participant interactions will occur online or via phone.

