## **19.0 Data Management and Analysis\***

*19.1 Describe the data analysis plan, including any statistical procedures. This section applies to both quantitative and qualitative analysis.*

Response:

Linear mixed models will be used to test effects of the interventions on total calories, carbohydrates, sugar (total sugar and/or added sugar), and nutritional quality of grocery purchases, with study group, time, and their interaction as factors. Primary comparisons will be between-groups comparisons of these variables at post-test. We will also examine whether these variables differ overall by study group and whether changes in these variables differ by study group. We will conduct each analysis once for the total cart and then again examining these variables relative to household size and for items that the respondent indicated they would be consuming. We will conduct parallel analyses with total dollars spent each week and with DASH diet scores as outcomes to examine effects on spending and intake. We will also explore whether effects differ for participants with prediabetes vs. diabetes and whether results change when adjusting for food purchases beyond the target stores. Finally, we will test for relationships between purchases (calories, carbohydrates, and sugar (total sugar and/or added sugar)) and intake (DASH diet scores). We will also explore whether results differ when considering shopping trips completed by the participant only (vs. all trips for the household).

*19.2 If applicable, provide a power analysis.*

*NOTE: This may not apply to certain types of studies, including chart/records reviews, survey studies, or observational studies. This question is asked to elicit whether the investigator has an adequate sample size to achieve the study objectives and justify a conclusion.*

Response:

To estimate the sample size needed for this study, effect sizes from the most similar existing study were used: a proof-of-principle study examining the effects of defaults, incentives, and education strategies on healthfulness of grocery purchases among undergraduate students (Coffino & Hormes, 2018, Obesity). Based on the observed differences in calories purchased at post-test between defaults and education control groups (Cohen's  $d=0.96$ ), 15 participants would be needed for the primary comparison in the present study, with  $\alpha=.05$  and  $\text{power}=.80$ . We repeated this analysis using the difference between controls and

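### The sections disagree on whether sex is a stratification factor, the mixed model adjusts for no stratification factor, and the exploratory prediabetes-versus-diabetes split does not match the strata

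*Combined protocol and SAP*

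**What the plan says.** **Stratification.** Section 1.0 (Study Summary) states: "Stratification factors will be sex and diabetes status: diabetic vs. at risk for type 2 diabetes". Section 5.1 agrees: "Stratification factors will be sex and diabetes status: type 2 diabetic vs. at risk for type 2 diabetes". Both put people with diagnosed prediabetes and people who are positive on the American Diabetes Association risk test into the at-risk category. Section 12.1, the operational text, says "Participants will be randomized in blocks to the" three arms, "stratifying by diabetes status (diabetes vs. increased risk for developing type 2 diabetes". It does not mention sex. Staff read each assignment from a spreadsheet prepared in advance. Block size and allocation ratio are not given.

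**Model.** Section 19.1 specifies linear mixed models "with study group, time, and their interaction as factors". It adds: "Primary comparisons will be between-groups comparisons of these variables at post-test". Overall group differences and group differences in change are also planned. No term for sex or diabetes status is listed.

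**Subgroup.** Section 19.1 also says: "We will also explore whether effects differ for participants with prediabetes vs. diabetes". Section 8.1 has three routes into the trial: type 2 diabetes, diagnosed prediabetes, or a risk-test score of 5 or more. Section 10.1 lets participants go forward on self-report while the physician's confirmation is still being sought.

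**The concern.** Three things that should agree do not: the factors used to allocate, the terms in the model, and the categories in the subgroup analysis.

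- A reader cannot tell whether the allocation list has two strata (diabetes status) or four (sex by diabetes status), so cannot tell which factors the analysis should carry.
- Stratified blocks remove chance imbalance between arms on the strata. A model without those factors still counts their variance as noise. Its standard error then describes a less balanced trial than the one that was run, and precision is lost in the primary comparison.
- Someone with a positive risk test and no diagnosis is randomised in the at-risk stratum but is neither "prediabetes" nor "diabetes" in the subgroup sentence. Unless the plan says how to classify that person, the choice will be made after the data are in hand.

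**Working it through.** The plan gives no figure on this point to reproduce: it does not say how prognostic the strata are, and the sample sizes in section 19.2 are unaffected.

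**1. What the allocation text implies.** With three arms and 100 people randomised (the maximum enrolment), section 12.1 gives 3 × 2 = 6 arm-by-stratum cells, averaging 100/6 = 16.7 people. Sections 1.0 and 5.1 give 3 × 4 = 12 cells, averaging 100/12 = 8.3. These are different allocation lists, and only the spreadsheet can show which one was used.

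**2. Effect of omitting the strata on the post-test comparison.** Inputs: alpha = .05 (section 19.2; taken as two-sided, since the plan does not say) and R², the share of post-test outcome variance explained by the factors actually used in allocation (assumed). With strata balanced across arms, the true variance of an arm difference is (1 − R²) times the variance that the unadjusted model reports. Therefore:

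- reported SE / true SE = 1/√(1 − R²)
- true alpha = 2[1 − Φ(1.96/√(1 − R²))]

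| Assumed R² | SE ratio | 1.96/√(1 − R²) | True alpha |
|---|---|---|---|
| 1% | 1.005 | 1.970 | .049 |
| 5% | 1.026 | 2.011 | .044 |
| 10% | 1.054 | 2.066 | .039 |
| 20% | 1.118 | 2.191 | .028 |

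**3. Check by simulation.** The simulation compared Defaults with control at post-test, with 100 randomised, stratified blocks of 6, both factors stratified and equally prognostic, and 4,000 runs per setting. The block size and equal allocation are assumptions. The Monte Carlo SE for alpha is about .003.

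| R² (both factors) | Alpha, factors omitted | Alpha, factors included | Power at d = 0.44, omitted | Power at d = 0.44, included |
|---|---|---|---|---|
| 10% | .037 | .046 | .43 | .48 |
| 20% | .032 | .057 | .42 | .51 |

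The omitted-factor results agree with the formula. The value .057 is about two Monte Carlo SEs above .05. The effect size d = 0.44 is the one that section 19.2 uses for its more conservative calculation.

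**4. If section 12.1 is right and only diabetes status was stratified.** Only the variance explained by diabetes status enters the formula. In the same simulation, with total R² of 10% and 20% split equally between the two factors, alpha with both omitted was .044 and .041. The formula at half those shares (5% and 10%) gives .044 and .039.

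**5. Change comparisons.** A stable difference between strata adds the same amount to a person's baseline and post-test values and cancels in the difference. In a separate simulation (32 per arm, exactly balanced strata, R² = 20%, within-person correlation at least .5), alpha with the factor omitted was .028 for the post-test contrast and .050 for the change contrast.

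**6. Subgroup categories.**

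| Route into the trial (section 8.1) | Stratum (sections 1.0, 5.1, 12.1) | Category in section 19.1 subgroup |
|---|---|---|
| Type 2 diabetes | Diabetes | Diabetes |
| Diagnosed prediabetes | At risk | Prediabetes |
| Risk test only | At risk | None stated |

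**The case against.** The strongest reply concerns size. The first-listed outcome is the household's total cart, while sex and diabetes status describe only the shopper. The strata may explain very little of that variance, and at R² of 1% the effect is negligible. This stands: the documents give no R², so the size has to be shown from near zero upwards, and a 10% to 20% share cannot be treated as established.

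The loss also does not reach every planned test. Hypothesis 1b and the change analyses rest on within-person differences, where a stable stratum effect cancels. This stands too.

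If sex was never a stratum, omitting it does not make the test conservative. That is correct: adjusting for sex would then be a choice about precision, not a consequence of the design.

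A reader might infer that risk-test-only participants are dropped from the subgroup analysis. Section 19.1 excludes nobody, and its wording may simply be an older label for everyone at risk. What the text supports is narrower: no category is stated for them. The analysis is also labelled exploratory.

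A reader might also infer that leaving out the strata biases the estimates or produces false positives. It does neither; the error is on the conservative side.

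**Conclusion.** The point holds within those limits. Two parts are firm on the current text and need no assumption: sections 1.0 and 5.1 contradict section 12.1 on sex, and the subgroup split does not match the strata or the eligible population.

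The third part, the absence of any stratification factor from the mixed model, is also plain in the text, but its cost is uncertain. For the primary post-test comparison and overall level comparisons, it runs from almost nothing (true alpha .049, standard errors 0.5% too large at R² of 1%) to a material loss (.028 and 12% at R² of 20%). In the simulated cases with both factors stratified, including them raised power at d = 0.44 by about 4 points at R² of 10% (.434 to .477) and 9 points at 20% (.415 to .506). These figures assume a two-sided .05 test, balanced strata and, for power, 100 randomised in equal arms. The change contrasts are little affected. The repair is worth making because it is cheap and can be fixed before any group comparison is seen.

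**What to change.** 1. Check the allocation spreadsheet and make sections 1.0, 5.1 and 12.1 state the factors actually used.
2. In section 19.1, add those factors, as randomised, as fixed effects in the mixed models. Diabetes status goes in either way, since all three sections name it. Sex goes in if it was a stratum; otherwise it is at most an optional precision covariate, specified in advance.
3. Define the exploratory subgroup as type 2 diabetes versus at risk, matching the strata and so including risk-test-only participants, and test it by interaction with study group.
4. Add a sensitivity analysis of that subgroup using physician-confirmed status, because section 10.1 allows people to proceed on self-report and status at randomisation may differ from status confirmed later.

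The cost is wording plus one or two degrees of freedom for the adjustment. Any factor used to allocate is already recorded, physician confirmation is already planned, and the sample size does not change.
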